3.8 STUDY PROCEDURES AND FLOWCHART

A schematic of the study design is provided below:

This study includes the following:

1. **Screening Period:** Day of Screening Visit until Day 1 (first dose of study drug). The Screening Visit can occur Day -38 to Day -5, relative to the first dose of study drug

2. Treatment Periods:

Part A:

- Treatment Period 1: Day 1 (first dose of study drug) through Day 29 (28 days of treatment)
- Washout Period: Day 29 through Day 56 (28 days)
- Treatment Period 2: Day 57 through Day 85 (28 days of treatment)

1006696
Parion Sciences Incorporated
CLEAN-PCD
SAP Version 1.0

Part B (Optional):

- Treatment Period 3: Day 85 (first dose of oral ivacaftor) through Day 113 (28 days of treatment)
3. **Safety Follow-up Period:** 28 days (\pm 7 days) after the last dose of study drug.

If the subject prematurely discontinues study drug, an Early Termination of Treatment (ETT) Visit should be scheduled as soon as possible after the subject decides to terminate study drug treatment. Subjects who prematurely discontinue treatment will also be required to complete the Safety Follow-up Telephone Call approximately 28 days (\pm 7 days) after their last dose of study drug.

If the subject meets the criteria for study participation and is taking HS at the time of Screening, the subject will be instructed to stop their usual regimen of inhaled HS for the duration of the study, beginning at least 28 days before the first dose of study drug in the study and continued through completion of the last study visit. If a subject is not taking HS as part of their ongoing PCD treatment, the Day 1 Visit may be scheduled to occur as soon as 5 days after the Screening Visit, provided that results of all screening procedures have been received. Each subject will be instructed to use an appropriate airway clearance technique throughout the study.

Schedules of Assessments are shown in [Appendix IV Table 5](#), [Table 6](#) and [Table 7](#)

1006696
Parion Sciences Incorporated
CLEAN-PCD
SAP Version 1.0

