6.2.2 Treatment Emergent Period

Treatment-emergent (TE) period for Part A Treatment Period 1:

1006696
Parion Sciences Incorporated
CLEAN-PCD
SAP Version 1.0

- The Treatment-Emergent Period will correspond to the interval from the first dose date of Treatment Period 1 to 28 days after the last dose date of Treatment Period 1 or the date before the first dose date of Treatment Period 2 or the safety follow-up visit, whichever occurs earlier.

TE period for Part A Treatment Period 2:

- The treatment emergent period will correspond to the interval from the first dose date of Treatment Period 2 to 28 days after the last dose date of Treatment Period 2 or the date before the first dose date of Part B or the safety follow-up visit, whichever occurs earlier.

Treatment-Emergent Period for Part B:

- The treatment emergent period will correspond to the interval from the first dose date of study drug in Part B to 28 days after the last dose date of Part B or the safety follow-up visit, whichever occurs earlier.

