Summaries will be presented by treatment and by MedDRA (version 18.1) system organ class (SOC) and preferred term using frequency counts and percentages (i.e., number and percentage of subjects with an event). When summarizing the number and percentage of subjects with an event, subjects with multiple occurrences of the same AE or a continuing AE will be counted once, only the maximum severity level will be presented in the severity summaries, and the worst/highest relationship level in the

1006696
Parion Sciences Incorporated
CLEAN-PCD
SAP Version 1.0

relationship summaries. An AE overview table will be provided for the following categories:

- TEAEs
- Related TEAEs (includes Related and Possibly Related)
- Serious TEAEs
- Related Serious TEAEs
- TEAEs Leading to Study Drug Interruption
- TEAEs Leading to Study Drug Discontinuation
- TEAEs with Outcome of Death

In addition, a listing containing individual subject AE data for all deaths and other serious AEs will be provided separately for Part A and Part B. All AEs, including pre-treatment AEs, will be presented in individual subject data listings.

TEAEs related to study device will also be summarized by system organ class and preferred term using frequency counts and percentages (i.e., number and percentage of subjects with an event).

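### Treatment-emergent AE windows are about 28 days for Period 2 of Part B entrants but about 56 days elsewhere, so crude percentages in Part A and Part B are not on the same footing

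*SAP*

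**What the plan says.** SAP 6.2.2 defines three treatment-emergent windows. Each opens at the first dose of its period and closes at the earliest of several dates, one of which is always the safety follow-up.

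- Period 1 closes at "28 days after the last dose date of Treatment Period 1 or the date before the first dose date of Treatment Period 2".
- Period 2 closes at "28 days after the last dose date of Treatment Period 2 or the date before the first dose date of Part B".
- Part B runs "from the first dose date of study drug in Part B to 28 days after the last dose date of Part B".

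The calendar is in SAP 3.8: "Washout Period: Day 29 through Day 56 (28 days"; "Treatment Period 2: Day 57 through Day 85 (28 days of treatment"; "Treatment Period 3: Day 85 (first dose of oral ivacaftor) through Day 113 (28 days of treatment". SAP 3.3 states that no washout separates Part A from Part B. Protocol 12.3.1 has the same structure: Period 2 of completers stops before the first Part B dose, and Part B runs to the end of the study.

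SAP 10.1 summarizes TEAEs by treatment, system organ class and preferred term, "using frequency counts and percentages (i.e., number and percentage of subjects with an event". Neither that section nor the safety summary in SAP 10.8 plans an exposure-adjusted rate, an on-treatment table or a common window. SAP 10 presents Part A by treatment received. Each Part A column therefore combines Period 1 of one sequence with Period 2 of its mirror sequence.

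**The concern.** Every window consists of 28 days of dosing plus up to 28 days off drug, except Period 2 of a subject who goes on to Part B. That subject loses the off-drug tail because the next dosing period starts at once. An event that starts on the changeover day is also counted in Part B (SAP 10.1).

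A crude percentage of subjects with an event rises with the length of observation. Adverse events belong to a primary endpoint of both Parts (SAP 4.1.1 and 4.2.1). Part B is not randomized and gives ivacaftor to everyone, so Part A is the only internal reference against which its AE percentages can be read. If Part A is observed for less time, Part B can show higher percentages when ivacaftor does nothing.

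Within Part A, the length of the Period 2 window also depends on an optional choice to enter Part B. If the mirror sequences enter at different rates, the treatment columns are observed for different lengths of time.

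**Working it through.** **The plan's own durations.** 85 + 28 = 113 days for Part A and 113 + 28 = 141 days for Parts A and B. Both agree with SAP 3.3.

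**Window lengths.** Length = closing date − first dose date + 1, on the planned calendar.

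| Cell | Dates (morning schedule) | Days |
|---|---|---|
| Period 1 | 1 to 56 | 56 |
| Period 2, Part B entrants | 57 to 84 | 28 (25 to 31 with the ±3-day visit window) |
| Period 2, non-entrants completing dosing | 57 to 112 | 56 |
| Part B | 85 to 140 | 56 |

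On the afternoon schedule the last two rows are 57 days. If the follow-up call comes at 21 days they are 49 or 50.

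**Mean window of a planned Part A column.** Let e be the proportion entering Part B. The documents do not give e, so it is an assumption. The two sequences that feed a column are of equal planned size (50 and 50, or 25 and 25), so

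mean window = 0.5 × 56 + 0.5 × [28e + 56(1 − e)].

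- e = 100%: 42 days
- e = 80%: 44.8 days
- e = 50%: 49 days

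The Part B window is 56 days.

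**Effect on percentages.** Assume no ivacaftor effect, a constant hazard on and off drug, and that all subjects complete dosing. Let p be the percentage with an event in 28 days (also an assumption). Then

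- 56-day percentage: q = 1 − (1 − p)²
- Part A column: 0.5q + 0.5[ep + (1 − e)q]

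For p = 30%: q = 1 − 0.7² = 51.0%. At e = 80%, Period 2 is 0.8 × 30 + 0.2 × 51 = 34.2%, and the column is (51.0 + 34.2)/2 = 42.6%.

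| p (28 days) | Part A, e = 100% | Part A, e = 80% | Part A, e = 50% | Part B |
|---|---|---|---|---|
| 10% | 14.5% | 15.4% | 16.8% | 19.0% |
| 20% | 28.0% | 29.6% | 32.0% | 36.0% |
| 30% | 40.5% | 42.6% | 45.8% | 51.0% |

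At p = 30% the ratio of Part B to Part A is 1.26, 1.20 and 1.11.

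**Lower hazard off drug.** If the hazard halves off drug, 28 + 28 days carry the risk of 42 days on drug: q = 1 − 0.7^1.5 = 41.4%. At e = 80%, Period 2 is 0.8 × 30 + 0.2 × 41.4 = 32.3%, and the column is (41.4 + 32.3)/2 = 36.9%. The gap is about 4.5 points, against 8.4 under constant hazard.

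**Within Part A.** Assume that 60% of sequence 2 and 80% of sequence 1 enter Part B, with p = 30% and constant hazard.

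- VX-371 in HS: Period 2 is 0.6 × 30 + 0.4 × 51 = 38.4%; column (51.0 + 38.4)/2 = 44.7%.
- HS alone: column 42.6%, as above.

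The difference is 2.1 points. With equal entry it is zero.

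**The case against.** **The 2:1 contrast is not in the planned tables.** A reader might infer from the windows that the AE tables set 28 days against 56, so that 30% would turn into 51%. The documents do not support this. No planned TEAE table isolates Period 2, still less Period 2 of Part B entrants. Pooling both periods by treatment reduces the contrast to about 42 to 49 days against 56. This stands, and the size given here is that of the pooled columns.

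**No claim about ivacaftor safety is planned.** A reader might also infer that ivacaftor will look harmful. The SAP presents the Parts separately and plans no AE comparison between them. Part B is offered to subjects who completed Part A treatment (SAP 3.5.2), and that selection may lower its percentages. The net direction is therefore not established. What remains is that the window length alone pushes Part B upward, and that readers have no other internal reference.

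**The definition is conventional.** Once ivacaftor starts without a washout, later events cannot sensibly be charged to Period 2 alone, and the protocol has the same rule. This stands as a defence of the attribution rule. It does not make the resulting percentages comparable.

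**A poorly tolerated treatment need not be watched longer.** Subjects who stop early are not offered Part B, but their window also closes by 28 days after their last dose. One who stops on day 7 has about 35 days (7 + 28), not 56. The within-Part A imbalance is therefore small unless completers of the mirror sequences enter Part B at clearly different rates.

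**Some mitigation exists.** All AEs are listed by subject (SAP 10.1), and treatment duration is summarized by treatment (SAP 7.6). Neither changes the denominator of the AE tables.

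**Conclusion.** The concern holds as a matter of comparability. The TEAE percentages rest on unequal windows: about 28 days for Period 2 of Part B entrants and about 56 days in the other cells for subjects who complete dosing. In the columns that the SAP will print, this is a mean of about 42 to 49 days in Part A against 56 in Part B, for entry rates from 100% down to 50%.

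At an assumed 30% rate in 28 days, window length alone is worth about 5 to 10 points under constant hazard. It is worth about 4.5 points at 80% entry if the off-drug hazard is half. At lower event rates the gap in points is smaller. These sizes rest on assumed event rates, entry rates and hazards, because the documents give none of them.

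The documents do not show that Part B percentages will in fact be higher, or that any planned analysis will reach a wrong conclusion about ivacaftor. Comparisons within Part A are little affected: about 2 points at a 30% rate if entry differs by 60% against 80%, and none if entry is equal.

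**What to change.** Keep the planned TEAE tables and add the following to SAP 10.1:

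1. By-treatment tables of on-treatment onsets, from first dose to last dose date, or to the day before the next period's first dose if that is earlier. For subjects who complete dosing this covers 28 or 29 calendar dates in every cell. With no ivacaftor effect and a constant hazard, the expected ratio of Part B to Part A is then about 1.0.
2. Onsets in washout and follow-up in separate columns, so that delayed events stay visible.
3. Events, or subjects with events, per 28 subject-days, because a first-to-last-dose window is shorter for subjects who stop early. Use on-treatment days as the denominator. A rate over the whole treatment-emergent window would mix on-drug and off-drug time: with half the hazard off drug, the average hazard over 56 days is (28 × 1 + 28 × 0.5)/56 = 0.75 of the on-drug hazard, which would understate Part B.

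State that any reading across treatments or Parts uses these tables, and that the Part B comparison remains uncontrolled and limited to Part A completers. The cost is one further set of AE tables from onset and dose dates already collected.

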6.3 MISSING DATA

Imputations for missing or partially missing start/end dates for prior/concomitant medications and adverse events are described in [Appendix V](#).

Imputation for missing individual QOL-PCD scores is described in [Appendix II](#).

[figure not shown]
No other imputations will be performed for missing data. Observed data will be used in the analyses.

6.4 VISIT WINDOWS

Visit windows can be found in [Appendix VI](#)

1006696
Parion Sciences Incorporated
CLEAN-PCD
SAP Version 1.0

7 DEMOGRAPHIC, OTHER BASELINE CHARACTERISTICS AND MEDICATION

7.1 SUBJECT DISPOSITION AND WITHDRAWALS

Part A

The number of subjects in the following categories will be presented by treatment group:

- All Subjects Set (randomized or dosed)
- Randomized (defined as subjects who were assigned a treatment sequence but have not necessarily taken a dose of study drug).
- Randomized but not dosed
- Full Analysis Set (FAS)
- Safety Set

The number of subjects in the following categories will be presented by treatment group for each period (Period 1 and Period 2):

- Full Analysis Set (FAS)
- Safety Set

The number and percentage (based on Part A FAS) of subjects in each of the following disposition categories will be presented by treatment group for each period (Period 1 and Period 2):

- Completed treatment regimen
- Prematurely discontinued the treatment and the reasons for discontinuation
- Prematurely discontinued the study and the reasons for discontinuation

The number and percentage (based on the overall FAS) of subjects in each of the following disposition categories will be presented by treatment group:

[figure not shown]
- Completed treatment regimen in both periods
- Completed study in Part A
- Rolled-over to Part B

A listing of subjects who discontinued study or discontinued treatment regimen for Part A will be provided.

Part B

1006696
Parion Sciences Incorporated
CLEAN-PCD
SAP Version 1.0

The number of subjects in the following categories will be presented by treatment group and overall:

- Full Analysis Set (FAS)
- Safety Set

The number and percentage (based on Part B FAS) of subjects in each of the following disposition categories will be presented by treatment group and overall:

- Completed Part B study drug treatment
- Prematurely discontinued Part B study drug treatment and the reasons for discontinuation
- Completed study in Part B
- Prematurely discontinued the study in Part B and the reasons for discontinuation

A listing of subjects who discontinued study or discontinued treatment regimen for Part B will be provided.

7.2 SUBJECT SCREENED AND SCREEN FAILURE

Screen failure for Part A is defined as any screened subject who was not dosed with study drug.

Number of screened subjects and number and percentages of screen failures will be summarized, and all screen failures will be listed with their corresponding screen failure reason.

A listing for randomized but not dosed subjects (a subset of screen failure subjects) will be provided.

7.3 DEMOGRAPHIC AND OTHER BASELINE CHARACTERISTICS

Demographic and baseline characteristics will be summarized for Part A and Part B.

The following demographics and study baseline characteristics will be summarized by Period 1 treatment and Period 2 treatment for Part A FAS and overall, treatment for Part B FAS and overall: sex, child bearing potential, race, ethnicity, age at baseline, age (<18 years old), weight, height, body mass index (BMI), region (North America and Europe), study baseline ppFEV1, nNO measurement (nNO level 1 and nNO level 2), laterality defect, ciliary ultrastructure defect, and PCD genetic mutation.

1006696
Parion Sciences Incorporated
CLEAN-PCD
SAP Version 1.0

In addition, Part B baseline characteristics will also be summarized based on Part B FAS by treatment group and overall, including age at Part B baseline, weight, height, BMI and ppFEV1.

7.4 MEDICAL HISTORY

Medical history will be coded using the Medical Dictionary for Regulatory Activities (MedDRA), Version: 18.1.

Medical history data will be summarized by Period 1 treatment and Period 2 treatment for Part A FAS and by treatment for Part B FAS.

7.5 MEDICATION

Medications will be coded using World Health Organization (WHO) DRUG dictionary, Version: WhoDrugDDEB2 201512 (ENG).

7.5.1 Prior Medication

Prior medication is defined as any medication that has a start date before the first dose of study drug in Part A, regardless of when it ended.

If the medication end date is before the date of first dose of study drug, then the medication will be summarized as prior medication regardless of whether the medication start date is missing or not.

Prior medications will be summarized by ATC level 1 and 2 term, preferred term (PT) and treatment for Part A and Part B separately.

7.5.2 Concomitant Medication

[figure not shown]
Concomitant medication is defined as any medication that is continued or newly received during the Treatment-Emergent (TE) period for Part A, or Part B.

A medication that starts/ends on or after the start date of the Treatment Emergent Period, up through and before the start date of the next Treatment Emergent Period, will be assigned to the treatment group associated with the current Treatment Emergent Period.

For the cases when Treatment Emergent Period 2 end of dosing is on the same day as the Treatment Emergent Period for Part B start of dosing date, any medication starting on the same day as the Treatment Emergent Period for Part B start of dosing date, will be assigned to the treatment in Period for Part B.

1006696
Parion Sciences Incorporated
CLEAN-PCD
SAP Version 1.0

A given medication can be classified as a prior medication, a concomitant medication, or both prior and concomitant. If a medication has a missing or partial missing start/end date and it cannot be determined whether the medication was taken before initial dosing or concomitantly, it will be considered as prior and concomitant, and this medication will be assigned to all treatment groups.

If the start date of the medication is the same as the date of the first dose date of the study drug in Period 1, then the medication is classified as a concomitant medication and will be assigned to Period 1 treatment group.

Concomitant medications will be summarized by ATC level 1 and 2 term and preferred term (PT). Part A concomitant medications will be summarized by treatment based on the Part A FAS, and Part B concomitant medications will be summarized by treatment based on the Part B FAS.

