### 8.1.1 Maintenance of Stable Medication Regimen for PCD

If the subject meets the criteria for study participation and is taking HS at the time of screening, the subject will be instructed to stop their usual regimen of inhaled HS for the duration of the study, beginning at least 28 days before the first dose of study drug in the study and continued through completion of the last study visit. If a subject is not taking HS as part of their ongoing PCD treatment, the Day 1 Visit may be scheduled to occur as soon as 5 days after the Screening Visit, provided that results of all screening procedures have been received. Each subject will be instructed to use an appropriate airway clearance technique throughout the study.

All concomitant medications and airway clearance measures/techniques should be kept on a stable regimen for the duration of the study, other than the discontinuation of use of HS during the Screening Period.

If taking daily chronic or chronic cycling antibiotics, the subject must have been on a consistent regimen for at least 4 months before the Screening Visit. The cycling regimen of antibiotics can be either intermittent monotherapy (e.g., 28 days on/28 days off) or continuous alternating therapy (e.g., 28-day cycles of 2 alternating antibiotics). For patients that take cycling antibiotics, with only 1 antibiotic, the first visit of Treatment Period 1 and Treatment Period 2 should be scheduled to occur on the same day of the subject's antibiotic cycle (e.g., if Day 1 falls on the 4th day of a cycle, Day 57 should fall on the 4th day of the same antibiotic cycle). For patients that take cycling, alternating antibiotics, the first day of Treatment Period 1 and Treatment Period 2 should be scheduled to occur on the same day of the subject's antibiotic cycle with the same drug (e.g., if Day 1 falls on the 4th day of a cycle with antibiotic #1, Day 57 should also fall on the 4th day of the cycle with antibiotic #1). Subjects who are on a stable chronic antibiotic regimen should remain on this regimen through completion of the last study visit.

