APPENDIX V HANDLING MISSING DATE

Prior/Concomitant medication:

Missing or partial medication start date:

- If only day is missing, use the first day of the month.
- If day and month are both missing, use the first day of the year.
- If day, month and year are all missing, use a date before the first dose date (in practice, use Jan. 01, 2000 to impute).

Missing or partial medication stop date:

- If only day is missing, use the last day of the month.
- If day and month are both missing, use the last day of the year.
- If day, month and year are all missing, assign 'continuing' status to stop date (in practice, use Dec. 31, 2050 to impute).

Adverse Event:

Imputation of missing AE start date:

- If AE start date is completely missing and AE end date is after the first dose date in Part A Period 1 but before first dose date in Part B, then use the first dose date in Part A Period 1 as the AE start date and classify the AE as a TEAE; if the AE end date is after the first dose date in Part B then
 - 1) Use the first dose date in Part A Period 1 as the AE start date
 - 2) Use the first dose date in Part B as the AE start date.
- If AE start date is completely missing, and AE end date is before the first dose date in Part A Period 1, then the AE is not a TEAE.
- If both AE start date and AE end date are completely missing then
 - 1) Use the first dose date as AE start date in Part A Period 1 and classify the AE as a TEAE for Part A
 - 2) Use the first dose date as AE start date in Part B and classify the AE as a TEAE for Part B

1006696
Parion Sciences Incorporated
CLEAN-PCD
SAP Version 1.0

Statistical Analysis Plan

- If only day is missing, use the first day of the month or the first dose date whichever is later, unless the AE start month is before the first dose date in which case, the AE start date remains missing and this AE is not a TEAE.
- If day and month are both missing, use the first day of the year or the first dose date whichever is later, unless the AE start year is before the first dose date. In this case, the AE start date remains missing and this AE is not a TEAE.

Imputed AE start date must be earlier than the original AE end date, otherwise set imputed start date = original AE end date and the AE is not a TEAE.

Missing AE causality

For summary tables of related AEs, report missing causality as 'related'.

Missing AE Severity

[figure not shown]
There will be no imputation of missing AE severity.

Missing SAE category

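### SAP 7.5.2 allocates concomitant medicines by start or end date and has no rule for a medicine that spans a whole treatment period (minor)

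*SAP*

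**What the plan says.** SAP 7.5.2 defines a concomitant medicine as "any medication that is continued or newly received during the Treatment-Emergent (TE) period for Part A, or Part B". Protocol 12.3.2.3 has the same definition but names Treatment Periods 1, 2 and 3. SAP Section 11 declares no change from the protocol.

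The next sentence of SAP 7.5.2 allocates medicines to treatment groups: "A medication that starts/ends on or after the start date of the Treatment Emergent Period", and then "up through and before the start date of the next Treatment Emergent Period, will be assigned to the treatment group associated with the current Treatment" TE period.

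Three further rules follow in that section:
- A medicine starting on the day of first dosing in Part B goes to the Part B treatment.
- A medicine starting on the day of first dosing in Period 1 goes to the Period 1 treatment.
- If missing dates leave it unclear whether a medicine was prior or concomitant, "it will be considered as prior and concomitant, and this medication will be assigned to all treatment groups".

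For a stop date that is missing altogether, Appendix V says to "assign 'continuing' status to stop date", using 31 December 2050 as the working value. Part A medicines are tabulated by treatment on the Part A FAS, and Part B medicines by treatment on the Part B FAS.

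**The concern.** The definition turns on use during a period. The allocation sentence turns on whether a start or an end falls within that period's window. The two agree for a short course but not for a medicine that runs through a period from one side to the other.

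Medicines of that kind are what the protocol expects. Protocol 8.1.1 says "All concomitant medications and airway clearance measures/techniques should be kept on a stable regimen for the duration of the study", and Table 9-2 keeps chronic and cycling antibiotics on the pre-study regimen in every period. Protocol 8.2.1 notes that antibiotics may affect spirometry, and ppFEV1 is the primary efficacy measure.

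The by-treatment table is the planned summary of background therapy on treatment. In a crossover, crediting a medicine to one period when it was taken in two puts it under one treatment and omits it from the other. In Sequence 1, a medicine credited to Period 2 only would be shown under HS alone and not under VX-371 in HS. In Sequence 2 the reverse would happen.

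**Working it through.** The plan gives no figure to reproduce, so the check applies the sentence to typical medication histories.

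**Inputs.** Nominal TE starts are Day 1 (Period 1), Day 57 (Period 2) and Day 85 (Part B), from SAP 3.8 and 6.2.2. The allocation windows are therefore Day 1 to before Day 57, Day 57 to before Day 85, and Day 85 onward. For a subject who does not enter Part B, the Period 2 window runs from Day 57 onward.

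**Rule as written.** Credit a period if TE start ≤ start date < next TE start, or TE start ≤ stop date < next TE start.

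**Overlap rule (the definition).** Credit a period if start date < next TE start, and stop date ≥ TE start or the medicine is continuing.

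**Two cases in full.**
- *Before Day 1 to Day 70.* Neither the start (before 1) nor the stop (70) lies in 1 to <57, so Period 1 is not credited. Since 57 ≤ 70 < 85, Period 2 is credited. By overlap, the start is before 57 and 70 ≥ 1, so Period 1 is credited as well.
- *Day 10 to Day 100, subject in Part B.* Since 1 ≤ 10 < 57, Period 1 is credited. Neither 10 nor 100 lies in 57 to <85, so Period 2 is not. Since 100 ≥ 85, Part B is credited. By overlap, 10 < 85 and 100 ≥ 57, so Period 2 is credited as well.

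| Medicine | Rule as written | Overlap |
|---|---|---|
| Before Day 1 to Day 70 | Period 2 | Periods 1, 2 |
| Day 10 to Day 100, enters Part B | Period 1, Part B | Periods 1, 2, Part B |
| Before Day 1, ongoing, enters Part B | Part B if the 2050 date counts as an end; otherwise none | Periods 1, 2, Part B |
| Before Day 1, ongoing, no Part B | Period 2 if the 2050 date counts as an end; otherwise none | Periods 1, 2 |
| Day 10 to Day 20 | Period 1 | Period 1 |

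**Do the other rules fill the gap?** The two same-day rules concern new starts only. The all-groups rule needs missing dates that leave the medicine's status undetermined, so it does not reach the first two rows, whose dates are complete. Read literally, a medicine with unclear dates is credited to every treatment, while a fully dated medicine taken across periods is credited to fewer.

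**The case against.** The strongest reply is that the sentence is not worded as exclusive. It does not say that a medicine belongs *only* where it starts or ends, and nothing in the SAP says that a continuing medicine is left out of a period. It could be a compressed overlap rule: ends on or after the TE start, and starts before the next one. The definition just above it, and the fuller one in the protocol, support that intent. The programming and table shells are not shown. This stands against any claim that the tables *are* wrong. It does not remove the gap: the definition settles whether a medicine is concomitant, not which column receives it, and no SAP sentence credits the Day 70 medicine to Period 1.

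A second reply is that the information appears elsewhere. Under SAP 7.5.1, any medicine begun before first dosing is a prior medicine whenever it ended, and is tabulated by treatment. All data are listed (SAP 6.1). This largely stands, and it lowers the severity. The prior-medication table does not, however, show whether use continued in each period, and it does not contain a medicine begun on study, such as the Day 10 to Day 100 case.

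A reader might also infer a definite under-count. If each Part A column drew equally on Periods 1 and 2, and the 2050 date counted as an end, the share of long-term users shown would be 0.5 × (1 − p), where p is the share entering Part B. That gives 50% at p = 0 and 0% at p = 1. The documents do not support using this as an estimate. They do not give p or the rate of use, and the formula assumes that Part B entry is unrelated to use. Appendix V supplies the 2050 date for wholly missing stop dates, and that date lies outside every TE period as SAP 6.2.2 bounds them.

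Nor can a threat to the efficacy result be inferred. The primary assessment, VX-371 in HS against HS alone, is made within subjects in Sequences 1 and 2, so a stable medicine is present under both treatments. The primary model in SAP 8.1 has no medication term. Adverse events have their own attribution rule in SAP 10.1.

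**Conclusion.** The allocation sentence is incomplete. If followed literally, it omits period-spanning medicines from some periods in which they were taken, contrary to the definition it is meant to apply. The result for the fully dated examples depends only on the wording and the nominal visit days. The result for ongoing medicines also depends on how the placeholder stop date is treated.

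The consequence is limited to the descriptive by-treatment concomitant-medication tables. None of the visible efficacy or adverse-event analyses uses the rule. The documents do not allow the under-count to be sized, and whether it occurs at all depends on programming that is not shown. Severity is minor.

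**What to change.** Replace the allocation sentence in SAP 7.5.2 with an overlap rule, for example:

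> Assign a medication to every treatment group for which (i) its start date, or imputed start, is before the first day of the next TE period (for the subject's last TE period, on or before the last day of that period), and (ii) its stop date is on or after the first day of the current TE period, or it is continuing.

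Keep the Day 85 same-day rule for new starts.

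Also state whether medicines taken only in the washout are credited to the Period 1 treatment or shown only in the SAP 7.5.3 washout summary. This matters because the Period 1 TE period ends no later than 28 days after the last dose (SAP 6.2.2), while Protocol 8.1.3.1.2 allows the washout to be extended by a further 28 days for respiratory infection. A course confined to that extension falls inside the current allocation window but outside the TE period. Bounding the rule at the TE end date for every period would drop such a course from the by-treatment table without saying so.

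The cost is one or two sentences and a small programming change, with no new data, to be settled before database lock. A long-term medicine will then appear under more than one treatment, which is correct in a crossover.
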